## Protocol Summary:

This is a prospective randomized, double-blinded, placebo-controlled, phase 2, three-month study of the efficacy of TPTD in postmenopausal women and men  $\geq 65$  years of age with acute fractures of the pelvis. We will extend this study with 9 months of open label TPTD to determine if any potential differences between the placebo and TPTD groups during the 3 months of treatment are evident and persist over time, even in patients who use TPTD after the three month placebo controlled intervention.

We will include men or women with single or multiple rami fractures and a presence or absence of sacral fracture. We will randomize 100 patients 1:1 in a blinded fashion to receive either 20mcg of TPTD subcutaneously (SC) every day or identically appearing placebo SC for 12 weeks. All patients will have ideal medical care for comorbidities, pain management and progressive mobilization. A routine clinical protocol will be followed to quickly normalize 25-hydroxyvitamin D (goal  $>20$  ng per milliliter; the current IOM guideline 201035) before starting treatment. All patients will receive a loading dose of vitamin D2 (at a dose of 50,000 IU given orally). After the loading dose, daily supplementation with 1000 IU vitamin D will be used for the duration of the study. This will allow for patients to be recruited and to begin the trial of TPTD or placebo within 2 weeks of the fracture with improved 25(OH)D levels. Calcium intake will be assessed and dietary suggestions or supplementation will be used to bring total intake to approximately 1000 mg a day, slightly lower than the recommended calcium intake for women over age 50 (in order to prevent hypercalcemia).

Our primary outcome is radiographic evidence of fracture healing at the 12-week endpoint. At 4, 8 and 12 weeks after initiating TPTD or TPTD placebo, all patients will get follow-up pelvic radiographs, although these radiographs will stop when healing occurs. If the radiologist notes cortical bridging on the monthly x-ray, or at 3 months a confirmatory limited low dose Focus CT at the fracture site(s) will be performed to assess the degree of bridging. Cortical bridging will be quantified with bridging of 3 or 4 cortices as "healing", 1 or 2 cortices as "partial healing", and 0 cortices as "minimal/no healing" by two independent radiologists and adjudication by a third. If there are multifocal fractures, cortical bridging at each site will be evaluated and an adjudicated score representing the state of healing (0 to 4) will be recorded. Secondary analysis will examine treatment group differences in the change in follow-up pelvic fracture healing scores over the repeated monthly assessments during the 3 month placebo-controlled phase.

A secondary outcome is pain and narcotic use. The numeric rating scale (NRS) will be administered by research staff that is blinded to treatment group. We will also quantify use of narcotics and other adjunct medications for pain by recording their reported use and also asking for narcotic bottles to be brought in at each visit and performing a pill count. The NRS and recording of pain medications will be done at baseline, 4, 8 and 12 week visits and at the 6, 9 and 12 month visits.

Another secondary outcome is lower extremity physical function at 3 months and again from 3-12 months. Physical performance tests will be administered by research staff that is blinded to treatment group. The lower extremity physical function tests, tests include normal walking speed over 4 meters (with or without an assistive device), repeated chair stands (stand up from a chair with their arms folded across their chest), and balance (ability to maintain balance for 10 seconds in each of 3 positions: side-by-side, semi-tandem, and tandem foot positions). In addition, the Timed Up and Go test will be completed by each subject. Each subject will also complete the survey of ADLs and the SF-36.

The primary outcome analysis is an ITT analysis of the categorization of the level of cortical bridging seen on focus CT at 3-months. The operational definition of cortical bridging is a five-level ordinal scale from "not healed" to "healed" (cf. protocol) adjudicated by the radiologists and clinicians, with two qualifications: 1) if endpoint assessment is missing because of a drop-out or loss-to-follow subsequent to an AE or SAE, the endpoint will be coded as "not healed"; 2) if the endpoint is missing for any other reason, the endpoint will be coded as the last available coding of the focus CT assessment. The treatment difference in cortical bridging will be evaluated by a 2x5 chi-square (group x score) with a trend test (Jonckheere-Terpstra) for the ordinal

level of bridging to see whether the TPTD treated participants “trend” to have a greater proportion of higher bridging scores than the placebo group.

Secondary analysis of the treatment group differences in the change in fracture healing scores across the 3-months of the placebo-controlled phase will use a generalized estimating equation for longitudinal repeated measures assuming a Poisson distribution with observation-level weighting from a logistic regression analysis of the missingness pattern following the approach used by Fitzmaurice, Lair and Ware (2011). The outcome will be coded as described for the primary outcome ITT analysis. Missing covariate values will be filled using the fully conditional specification multiple imputation method to impute a monotonically missing data pattern: outcomes will not be imputed. Continuous covariates will use the predictive mean matching method while classification covariates will use a logistic regression method.

For the secondary outcome of pain, we will use a between-groups linear mixed model for repeated measures (LMMrm) to estimate the between-group difference in the mean within-subject change from baseline to the end of the placebo controlled trial (0-3 months) and again to explore change from 3 to 12 months in the open label extension. Narcotic and non-narcotic pain medication use will enter the model as time-dependent covariates. Separately, treatment group differences in the cumulative narcotic and non-narcotic drug exposure in the 3-month placebo-controlled phase will also be estimated with linear mixed model for repeated measures. This analysis addresses the two questions, “Do patients treated with TPTD show more rapid reduction in reported pain level than those not so treated? If so, when?”

For the secondary outcome of lower limb physical function, we will use a between-groups linear mixed model for repeated measures (LMMrm) model for the analysis to estimate the difference in within-subject change from 0 to 3 months in the CSPP score in the two groups. A secondary analysis for this aim will explore the changes in physical function from 3 to 12 months in the two groups.

If TPTD can improve fracture healing, this study will have an impact on the treatment of persons with pelvic fracture who are not surgical candidates and often face severe pain, chronic immobility, and loss of function in the elderly. A positive finding of accelerated healing of pelvic fractures would also encourage study of TPTD for treatment of other osteoporotic fractures.

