**Statistical Plan:** There will be no interim analysis and missing outcome data will not be imputed. Statistical analysis will be performed using SAS software (Cary NC). Between group differences at baseline will be compared with t-tests or Wilcoxon rank sum tests and chi-square tests as appropriate (p-value <0.05 for significance). Randomization by the method of randomly permuted blocks will be created for gender and BP use groups. Our primary analysis is ITT analysis and our primary outcome (SA#1) is the categorization of the level of bridging seen on focus CT into the scores from 0 to 4, described above between 0 and 3 months. The difference in cortical bridging will be evaluated by a 2x5 chi-square (group x score) with a trend test (Jonckheere-Terpstra) to see whether TPTD treated "trend" to have more higher bridging scores than the placebo group. We expect 30% - 50% superiority with TPTD at 3 months. This categorical outcome will be further analyzed with generalized estimating equations (GEE) for longitudinal repeated measures assuming a Poisson distribution with weighting from logistic regression analysis of the missingness pattern. Secondary analyses of covariates, sensitivity analyses and the "per protocol" analysis will incorporate the aforementioned approach into this aim's GEE analysis. This analysis addresses the question "Do patients treated with TPTD show more rapid fracture healing than those given placebo? For SA #2, we anticipate that the difference in pain score between the TPTD and placebo groups in the proposed study will be > 30% at each monthly time point (0-3 months). We will use a between-groups linear mixed model for repeated measures (LMMrm) to estimate the primary outcome of the difference in the mean within-subject change from baseline in the two groups at the end of the placebo controlled trial (0-3 months) and again to explore change from 3 to 12 months in the open label extension. In addition, narcotic and non-narcotic pain medication use will enter the model as time-dependent covariates. This analysis addresses the two questions, "Do patients treated with TPTD show more rapid reduction in reported pain level than those not so treated? If so, when?" For SA#3, the CSPPS is the outcome. A linear mixed model for repeated measures (LMMrm) will be used with fixed effects of treatment group (TPTD vs. placebo), time (D1, 4-, 8- and 12-wk) and their interaction, the baseline level of the CSPPS and days from injury to randomization entered as covariates, and a within-subject covariance structure selected by empirical methods prior to hypothesis testing. This plan will be repeated for the "per protocol" analysis in which subjects are limited to those showing 80% or greater compliance over the 12-week trial. This statistical plan addresses the two clinical questions, "Do patients treated with TPTD recover lower limb function faster than those not so treated? If so, when?" LMMrm will be used to analyze data from 3-12 months and assess group by time interaction. We will group on prior BP exposure strata to account for possible heterogeneity in the R-side covariance structure.

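### The Protocol Summary fills in missing week-12 healing scores in the primary ITT analysis, the Statistical Plan says missing outcomes are not imputed, and nothing reconciles the two

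*Combined protocol and SAP*

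**What the plan says.** The Protocol Summary (primary outcome analysis) attaches two qualifications to the five-level week-12 bridging score.

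- Rule 1 assigns the not-healed category: "if endpoint assessment is missing because of a drop-out or loss-to-follow subsequent to an AE or SAE, the endpoint will be coded as" that category.
- Rule 2: "if the endpoint is missing for any other reason, the endpoint will be coded as the last available coding of the focus CT assessment".

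For the secondary GEE analysis, the same section says "The outcome will be coded as described for the primary outcome ITT analysis". Its sentence on covariates then says the method will "impute a monotonically missing data pattern: outcomes will not be imputed".

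The Statistical Plan (section 7) opens with "There will be no interim analysis and missing outcome data will not be imputed". In the same paragraph it says "Our primary analysis is ITT analysis and our primary outcome (SA#1) is the categorization of the level of bridging seen on focus CT", and it neither repeats the two rules nor refers to them. The Sample Size Justification recruits 100 to obtain 80 analyzable subjects who complete three months.

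The imaging text decides which scores exist:

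- **Before week 12**, a focus CT is done only if the x-ray shows bridging (Follow-up visits). The first scan is a standard pelvic CT (CT imaging).
- **When imaging stops.** The Protocol Summary says of the monthly radiographs "although these radiographs will stop when healing occurs", and Table 2 also runs imaging until healing. "Cortical bridging will be quantified with bridging of 3 or 4 cortices as" healing. Follow-up visits and Focus CT Scan (Follow-up) stop imaging at full union.
- **At withdrawal**, a final x-ray and focus CT are requested if the subject consents and none was done within a month (Withdrawals).

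**The concern.** Coding a leaver as not healed and carrying a last score forward both put a value where none was observed at week 12. An analyst who follows the Protocol Summary analyses up to 100 subjects. One who follows the Statistical Plan alone may analyse only those with an observed score, planned at about 80. The two can report different Ns, estimates and p-values for the primary outcome, and the choice could be made after the data are seen.

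Two smaller problems lie in the rules themselves. Rule 1 makes no exception for an earlier adjudicated focus CT, so an observed score can be replaced by the worst one. Rule 2 needs a focus CT to carry forward, and some early leavers will have none.

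**Working it through.** **Inputs from the plan.** 100 randomised 1:1, so 50 per arm. Overall drop-out is 20%, taken as 10 per arm. Healed at three months: 100% TPTD, 60% placebo. Alpha is 1%, with sidedness not stated.

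**Assumptions.** Two-sided test; equal drop-out in the arms; rule 1's not-healed code counts as a failure. The share *a* of drop-outs that follow an AE or SAE is not given, so it is varied. The plan also does not say what score non-AE leavers would carry forward, so two cases are shown: (A) the planned three-month rates, 100% versus 60%; (B) the week-8 rates quoted for the Timed Up and Go calculation, 100% versus 9%.

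**1. The plan's own figure.** 40 per arm, 100% versus 60%, two-sided 1%, by exact enumeration of the two binomials: power is 99.8% (Fisher) and 99.9% (chi-square). A normal approximation gives 98.6%. The stated figure of more than 95% is correct.

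**2. No coding.** Completers only: 40/40 versus 24/40, a difference of 40 points on N = 80.

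**3. With the two rules, 50 per arm.**

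- TPTD healed = [40 × 1.00 + 10(1 − a) × 1.00]/50
- Placebo healed = [40 × 0.60 + 10(1 − a) × c]/50, with c = 0.60 in case A and c = 0.09 in case B

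| AE share a | TPTD | Placebo, A | Difference, A | Placebo, B | Difference, B |
|---|---|---|---|---|---|
| 0 | 100% | 60% | 40 | 49.8% | 50.2 |
| 0.5 | 90% | 54% | 36 | 48.9% | 41.1 |
| 1 | 80% | 48% | 32 | 48% | 32 |

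The bottom row needs no carry-forward assumption, because rule 1 then covers every leaver. In the other rows the answer depends on the scores carried forward.

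**4. Power at 50 per arm, two-sided 1% (Fisher to chi-square, exact).** 80% versus 48%: 72.9% to 79.3%. 90% versus 54%: 92.5% to 95.0%. 90% versus 48.9%: 97.5% to 98.5%.

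**5. Rule 1 and earlier scores.** Take a subject with an adjudicated score at week 4 or 8, short of full union, who then leaves after an AE and has no later CT. Under the full-union stopping wording a week-12 CT was still due, so it is missing because of the drop-out, and rule 1 applies whatever was observed. The withdrawal scan may not help, since none is requested if one was done within a month.

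**6. Rule 2 and no scan.** Take a subject with no bridging on x-ray who leaves for a non-AE reason and has no withdrawal CT. There is no focus CT, and no bridging score is described for the standard CT at screening. Rule 2 returns nothing. A completer whose imaging stopped after full union is not affected: rule 2 carries that score forward.

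**The case against.** The strongest reply is that the sections agree. The Protocol Summary presents the rules as part of the operational definition of the endpoint. For the GEE it says in one paragraph that the outcome is coded by these rules and that outcomes will not be imputed. That suggests the authors keep the word impute for model-based filling, and calling the analysis ITT sits badly with a completers-only set. This softens the point, and a reader who infers a flat contradiction goes further than the text allows. It does not remove the point: the usage is never defined, the Statistical Plan does not refer to the rules, and the sample size is built on completers.

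A reader might also infer that rule 1 would erase healed results almost entirely in the TPTD arm. The documents do not support that. Once full union stops imaging, the week-12 CT is arguably absent by design and not because of drop-out, so rule 1 need not apply. If imaging stops at three or four bridged cortices, the same argument covers every healing score. The clear case is an observed score short of full union, and the plan gives no figure for how often that occurs.

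The rule 2 gap is narrow, because a withdrawal CT is requested. It needs a non-AE leaver without x-ray bridging who has no such scan.

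Finally, the figures are binary while the primary test is ordinal, and case B borrows rates from a non-randomised, unblinded study of a different peptide. Both criticisms stand.

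**Conclusion.** The point holds as an unresolved inconsistency that should be fixed. Whether the primary analysis has about 80 or up to 100 subjects, and what it estimates, depends on which section is followed. At the planned rates with 20% drop-out in each arm, the difference falls from 40 to 32 points, and two-sided 1% power from over 99% to 73–79%, if every drop-out follows an AE. That is an extreme case. With half after an AE, the difference is 36 or 41 points depending on the scores carried forward, so it cannot be said that the coding always shrinks the effect, or that it enlarges it.

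Nor does this show that the sample size is wrong: the stated power for 40 completers per arm is correct. The sizes rest on assumed AE shares, equal drop-out and a healed/not-healed outcome; the planned Jonckheere-Terpstra test was not modelled. Coding AE leavers as not healed is a legitimate conservative choice and is not itself the fault. The overwriting of observed scores and the rule 2 gap are secondary and are not quantified separately.

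**What to change.** 1. Replace the Statistical Plan's sentence with one saying that there is no imputation beyond the week-12 coding rules of the primary ITT analysis and that N is all randomised. Cross-refer to the Protocol Summary.
2. State that a subject whose imaging ended by design after adjudicated full union keeps that score, whether or not they later leave. For all other AE/SAE leavers keep rule 1 as primary. Add a sensitivity analysis in which every earlier adjudicated focus CT score from 0 to 4 stands; protecting only healing scores would keep the favourable observations and discard the rest.
3. Under rule 2, score as 0 the non-AE leavers who have no x-ray bridging and no focus CT, including those with no follow-up imaging. Add a sensitivity analysis such as multiple imputation.
4. Reconcile the imaging-stop wording in the Protocol Summary, Follow-up visits, Table 2 and Focus CT Scan (Follow-up).

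The cost is a few sentences and minor programming. Keeping full-union scores may mainly credit the arm that heals faster, so the result with rule 1 applied to all AE leavers should be shown beside it.

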fracture patients given 1-84PTH were healed within 12 weeks compared to 68% of the controls. However, there is not sufficient evidence at this time to recommend routine use of PTH peptides for fracture healing. Pelvic fractures are ideal to study for the impact of Teriparatide (TPTD) on rate of fracture healing because there are no surgical repairs for the vast majority of the fractures. Prior studies of TPTD on wrist fracture healing were limited and confounded by the increased prevalence of surgical fixation to treat these fractures. Strong evidence of pelvic fracture healing that may result from this study may not only have an impact on pelvic fractures but perhaps may indicate a potential use for other fractures as well.

In our proposed randomized, double blind, placebo controlled clinical trial in patients >65 years of age with acute pelvic fracture, we plan to evaluate whether treatment with daily subcutaneous TPTD 20 mcg/day compared with placebo, in addition to standard treatment (pain management, bed rest and prevention of complications from comorbid conditions), is effective in accelerating fracture healing in women and men compared to standard treatment alone. We hypothesize that development of a successful adjunctive therapy (TPTD) will accelerate radiographic evidence of fracture healing and speed functional recovery. If this hypothesis holds true, it would lead to a change in clinical practice and an improved quality of care for pelvic fracture patients. Evidence of an impact on the healing of pelvic fractures may also extend to a potential to improve healing of other osteoporosis-related fractures. In the planned trial we will recruit women and men with acute pelvic fractures and address 3 specific aims over 3 months of treatment in a placebo controlled double blind study to determine if **TPTD** in addition to standard care **versus placebo** and standard care:

1. Results in **earlier evidence of cortical bridging** on routine radiographs followed by confirmatory Focus CT, a novel method to reduce radiation exposure from CT scans (primary outcome).
2. Leads to **a faster reduction in pain** as assessed by both the Numeric Rating Scale and a reduction in the use of narcotics (secondary outcome).
3. Leads more to a more rapidly **improved functional outcome** using a short physical performance battery to assess lower extremity function (secondary outcome).

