in a randomized controlled trial of 102 postmenopausal women who had sustained a distal radial fracture. The authors concluded that their result should be interpreted with caution and noted that there was no further improvement with the 40 mcg dose. This provides rationale for our using a dose of 20 mcg TPTD per day. A recent study reported the successful use of PTH 1-84 to enhance the healing of fractures of the pubic ramus in 65 patients, based on x-ray and CT images. This study was not randomized or blinded and is therefore subject to bias, particularly since patients in the PTH 1-84 treatment group were treated at a single center, and patients from both this center and another center served as controls (no PTH 1-84 treatment). In that study, 100 mcg of PTH 1-84 (equivalent to about 40 mg TPTD) resulted in fracture healing at a mean of 7.8 weeks, and 100% of the treated group had healed at 8 weeks following PTH1-84 administration, significantly faster than the control group (9% healed at 8 weeks and 68% at 12 weeks). Results of that study need to be confirmed for several reasons. First, a randomized, controlled, blinded study is required. Second, there may be some difference between 1-84PTH and 1-34PTH, as illustrated in a small study comparing the effects of these two peptides on cortical porosity assessed by high resolution pQCT. However, it does add to the growing clinical evidence that PTH peptides may improve fracture healing and also may improve physical function (using the Timed Up and Go test). Recent reviews and case series of TPTD and fracture healing state that there is a potential benefit of TPTD but all conclude that further randomized, placebo controlled, clinical trials are warranted. An important additional question is whether the benefit of TPTD on fracture healing wanes over time. In a recent study, improved mobility was seen at 3 and 6 months but not 12 months in TPTD treated patients with unstable pertrochanteric fractures, making a longer follow-up important in the proposed trial.

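### Aim 2 asks whether pain falls faster on TPTD, but the only blinded-phase NRS contrast the plan names is the change from baseline to the end of month 3

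*Combined protocol and SAP*

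**What the plan says.** Section 2 (Trial Objectives and Purpose) states Aim 2 as "a faster reduction in pain", assessed by the NRS and by narcotic use.

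The Protocol Summary schedules the measurement: "The NRS and recording of pain medications will be done at baseline, 4, 8 and 12 week visits". Table 2 agrees.

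The Protocol Summary's paragraph on the pain outcome says the linear mixed model will "estimate the between-group difference in the mean within-subject change from baseline to the end of the placebo controlled trial (0-3 months". Section 7, Statistical Plan, SA#2, gives the same quantity and ranks it: "primary outcome of the difference in the mean within-subject change from baseline in the two groups at the end" of the blinded phase. Both places then say that the analysis answers "Do patients treated with TPTD show more rapid reduction in reported pain level than those not so treated? If so, when". The Statistical Plan also expects that "the difference in pain score between the TPTD and placebo groups in the proposed study will be > 30% at each monthly time point".

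Treatment, time and their interaction are written out as fixed effects for SA#3 (CSPPS). Sample Size Justification names a treatment effect and an interaction for the Timed Up and Go. Section 4, Open Label Extension, names a group-by-time interaction for persistence to 12 months. For NRS in months 0 to 3, the plan names no week-4 or week-8 contrast, average over visits, slope or interaction test.

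**The concern.** The question and the named contrast do not match. A change from baseline to week 12 says how far pain has fallen by then, not how quickly it fell. Two arms can reach the same week-12 level with one of them weeks ahead, and this contrast would then be zero.

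If the benefit is early, the result ranked first for Aim 2 does not register it. If the benefit is present at every visit, as the plan expects, the contrast takes most of its information from one of three post-baseline visits and loses power. In both cases a choice of another contrast made after seeing the data would be post hoc. The healing aim is better served: it has an endpoint test and also a named longitudinal analysis.

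**Working it through.** **The plan's own figures.** There is no power statement for NRS to reproduce. The stated power concerns healing: 100% v 60%, 40 per group, 1% alpha, above 95%. Check (two-sided, normal approximation): null SE = √(2 × 0.8 × 0.2 / 40) = 0.0894; alternative SE = √(0.6 × 0.4 / 40) = 0.0775; (0.40 − 2.576 × 0.0894) / 0.0775 = 2.19, so power is 98.6%. The figure reproduces but says nothing about pain.

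**Inputs from the documents.** 40 analyzable per arm (100 randomized 1:1, 20% dropout); NRS at weeks 0, 4, 8 and 12; an expected difference above 30% at each monthly visit; missing outcomes not imputed.

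**Assumptions.** NRS SD 2.5; equal between-visit correlation r of 0.3 to 0.7; two-sided 5%; effect 1.2 points (30% of an assumed placebo mean of 4); unadjusted change; no medication covariates.

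**Step 1: standard errors.**
- Week-12 change: SE = SD × √(2(1 − r) × 2/40)
- Change averaged over three visits: SE = SD × √(((1 + 2r)/3 + 1 − 2r) × 2/40)

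The bracket in the second line simplifies to 4(1 − r)/3. The variance ratio is therefore [4(1 − r)/3] / [2(1 − r)] = 2/3, whatever the SD or r. For a constant effect, averaging is worth the same as going from 40 to 40 × 1.5 = 60 per arm.

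**Step 2: power for a constant 1.2-point effect**, Φ(1.2/SE − 1.96).

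| r | SE, week 12 | SE, average | Power, week 12 | Power, average |
|---|---|---|---|---|
| 0.3 | 0.661 | 0.540 | 44% | 60% |
| 0.5 | 0.559 | 0.456 | 57% | 75% |
| 0.7 | 0.433 | 0.354 | 79% | 92% |

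Range over SD at r = 0.5:
- SD 2.0: SEs 0.447 and 0.365, power 77% v 91%.
- SD 3.0: SEs 0.671 and 0.548, power 43% v 59%.

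**Step 3: other shapes of effect.** Same SD and n, 1.5-point lead, equal correlation 0.3 to 0.7 or AR(1) 0.7.
- Lead at weeks 4 and 8, matched by placebo at week 12: week-12 contrast 5%; average 46–81%; 3-df treatment-by-time test 77–99%.
- Lead sustained at all three visits: week 12 62–93%; average 79–99%; 3-df test 64–96%.
- Effect of 1.2 points at week 12 only (r = 0.5): the averaged effect is 1.2/3 = 0.4, and Φ(0.4/0.456 − 1.96) = 14%, against 57% for week 12.

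**Step 4: what weeks 4 and 8 contribute to the week-12 contrast.** With complete data, unstructured means and covariance and no time-varying covariates, they contribute nothing: at r = 0.5 and 50 per arm the per-arm variance is 2(1 − 0.5)/50 = 0.0200 per unit variance with or without them. With 20% dropout, removing them raises the variance by 1.0% to 4.4% if half of the dropouts are last seen at week 4 and half at week 8, and by 1.2% to 6.5% if all are lost after week 8.

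**The case against.** The strongest reply is that the model is longitudinal and is said to answer when the difference arises. Visit-level estimates are therefore implied, and the interaction terms written for CSPPS and the Timed Up and Go suggest how the pain model would be built; the plan adds that other outcomes are handled similarly. This stands as far as estimation goes. A reader might infer that an early benefit would be missed altogether, and the documents do not support that. What they lack is a named pain test of it.

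Three further inferences also go too far.
- **That the week-4 and week-8 data add nothing.** With the planned dropout they add a little (Step 4), and they also enter through the time-dependent medication covariates. The documents say only that these visits are scheduled, not that the data will be complete.
- **That Aim 2 as a whole would come out negative.** The aim also rests on narcotic use, and the Protocol Summary separately analyzes cumulative narcotic and non-narcotic exposure over the three months. An early benefit that reduced drug use would remain in that measure. The plan sets no decision rule for the aim.
- **That the arms will largely have converged by week 12.** This leans on control healing of "9% healed at 8 weeks and 68% at 12 weeks" in the cited non-randomized study of PTH 1-84. The plan's own sizing uses 60% for placebo, a 40-point gap at week 12, and Timed Up and Go values of 22.9 v 54.3 with SD 18, which is 31.4/18 = 1.7 SD apart. Tying pain to the healing gap also requires an assumed number of NRS points per healed fracture and an assumed zero effect at week 4, which contradicts the expected difference at each visit. Under such assumptions (3 points per healed fracture, r = 0.5), power is 40% v 77% with a 32-point gap and about 57% v 82% with the plan's 40-point gap. The case does not need this scenario.

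Finally, an average over visits is itself a level, not a speed. A treatment-by-time test is more sensitive to a transient lead, but less powerful than the average for the sustained difference that the plan expects (Step 3).

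**Conclusion.** The mismatch is real and worth correcting, at the weight of a secondary aim. The one blinded-phase NRS contrast that is named, and ranked first for SA#2, does not address speed. It has only alpha-level power for an early lead that placebo later matches. Under a constant effect it has 1.5 times the variance of the three-visit average; that ratio depends on equal correlation between visits but not on the SD or the correlation. The power differences (57% v 75% at r = 0.5, 44% v 60% at 0.3, 79% v 92% at 0.7) are illustrative, because the SD, correlation and effect in points are assumptions. The average leads for both the constant and the transient pattern, and loses when the effect appears only at week 12.

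**What to change.** In the pain paragraph of the Protocol Summary and under SA#2 in the Statistical Plan:

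- Write out the NRS model with treatment, time and treatment-by-time terms.
- Name as the lead SA#2 contrast the TPTD-minus-placebo difference in NRS change averaged equally over weeks 4, 8 and 12, from that same model.
- Report the three visit-specific differences, including week 12, with confidence intervals to answer the question of when.

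The equal average should not be described as the area under the pain curve: the trapezoid rule over weeks 0 to 12 gives 4 × week 4 + 4 × week 8 + 2 × week 12, that is, weights of 4:4:2.

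The cost is a short change in two places, with no new data or visits. The downside is lower power than week 12 alone if the effect appears only at week 12 (14% v 57% in the illustration). The plan does not expect that pattern, and the week-12 difference would still be reported.
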